## 10.2 Data Collection

Data collection requirements are summarized in **Table 7**. In addition, a surgeon experience survey (**Appendix 18.9**) will be conducted after the first procedure and after the tenth procedure. If the surgeon conducts fewer than ten procedures in the study, the second survey will be conducted after the final procedure. The ACHQC questionnaire is available in **Appendix 18.10**.

**Table 7. Data Collection and Study Procedure Requirements at Subject Visits**

Procedure/Assessment	Screening (Day -30 to 0) Visit 1	Surgical Procedure (Day 0) Visit 2	Hospital Discharge Visit 2.1	Follow-Up (30±7 Days) Visit 3	Follow- Up (3- Months ±14 Days) Visit 4	Follow-Up (Years 1-2 ±30 Days) Visit 5-6 (Phone)
	May be Combined					
Informed Consent Form 	X					
Eligibility Criteria	X	X				
Demographic Data	X					
Medical/Surgical History	X					
Concomitant Medication(s)	X	X	X	X	X	X
Robot Setup Time		X				
Total Operative Time (skin to skin)		X				
Surgeon Console Time		X				
Instruments Used		X				
Estimated Blood Loss		X				
Transfusion 		X	X	X	X	
Conversion to a laparoscopic, open surgery, or use of an alternative robotic-assisted system		X				
Robot Take Down Time		X				
Mortality			X	X	X	X
Length of Hospital Stay			X			
Reoperation			X	X	X	X
Pain Medication 			X	X	X	X
Adverse Events and Device Deficiencies 	X	X	X	X	X	X

*Medtronic Business Restricted*

**CONFIDENTIAL**

056-F275 Rev G Clinical Investigation Plan Template

# Enable Hernia Repair Clinical Investigation Plan

MDT21022

Version 5.0

Page 45 of 116

Medtronic

Readmission				X	X	X
Recurrence				X	X	X
Device Accountability		X				
ACHQC Questionnaire	X			X	X	
Protocol Deviation Collection (if applicable)	X	X	X	X	X	X
Study Exit						X

Study specific procedures may only be performed after subject has agreed to participate and signed the informed consent form. Screening and informed consent are considered as a process that may occur over multiple days within 30 days prior to procedure. Any new information about the subject's eligibility and willingness to participate must be considered prior to the procedure with the investigational device.

AEs must be followed until resolution or study exit, whichever comes first. Adverse Events will be collected from the moment of consent. If any events are ongoing at study exit, they will be monitored by the physician per their institutional standard-of-care. Refer to section 12 for AEs and DDs collected in scope of this study.

Transfusion will only be collected when associated with an adverse event.

 Pain medication(s) must be reported if given when pain is reported as an AE.

Note: The target number of days for the 3-month, 1-year, and 2-year visits is 90 days, 365 days, and 730 days post-procedure, respectively.

## 10.3 Subject Screening

Consented subjects will be considered for the study if they meet specified inclusion criteria and none of the exclusion criteria. The criteria for enrollment must be followed explicitly.

## 10.4 Prior and Concomitant Medications/Therapies

Institutional standard of care (SoC) pre-operative protocols and guidelines are typically in place to manage medications and are not reportable for the purposes of this study. Follow the guidelines below to report medications relevant to this study:

- Report applicable pre-procedure medications if taken within 30 days of the study procedure as listed in **Section 10.4.1 and 10.4.2**.
- Pain medication(s) must be reported if given when pain (Clavien-Dindo Grade I or higher – pain exceeds that which is considered within normal limits) is reported as an AE.
- Medications given during the procedure and/or post-procedure as treatment or preventative that result in a reportable AE should be captured.

For study purposes, reporting of the following drugs are required to evaluate potential AEs and endpoints.

*Medtronic Business Restricted*

**CONFIDENTIAL**

056-F275 Rev G Clinical Investigation Plan Template

## 10.4.1 Anticoagulants Taken within 30 Days Prior to Surgery

Prescription anticoagulants may include:

- Warfarin (Coumadin)
- Enoxaparin (Lovenox)
- Clopidogrel (Plavix)
- Ticlopidine (Ticlid)
- Aspirin (in many versions)
- Non-steroidal anti-inflammatory (NSAIDs) (in many versions)
- Dipyridamole (Persantine)

Non-prescription (over-the counter or herbal) anticoagulants may include:

- Non-steroidal anti-inflammatory (NSAIDs) (in many versions)
- Vitamin E
- Garlic
- Ginger
- Ginkgo biloba

## 10.4.2 Monoamine Oxidase Inhibitors (MAOIs) Taken within 30 days Prior to Surgery

MAOIs may include:

- Tranylcypromine (Parnate, Sico-ton)
- Phenelzine (Nardil, Nardelzine)
- Isocarbo-nazid (Marplan)
- Rasagiline (Azilect)
- Selegiline (Eldepryl, Deprenyl)
- Linezolid (Zuvon) (an antibiotic)
- St. John's Wort

In addition to the above, any medication given because of a study reported adverse event will be reported. Exclude the reporting of antiemetics, antipyretics, analgesics, diuretics and electrolytes and physiotherapy when given per standard of care procedures and/or within normal limits (dosage and frequency).

*Medtronic Business Restricted*

**CONFIDENTIAL**

056-F275 Rev G Clinical Investigation Plan Template

## 10.5 Subject Consent

Informed consent is defined as a legally effective documented confirmation of a subject's voluntary agreement to participate in a particular study after information has been given and explained to the subject on all aspects of the study that are relevant to the subject's decision to participate. This process includes obtaining an IC form that has been approved by the study site's IRB and signed and dated by the subject or their legally authorized/designated representative or guardian. A subject may only consent after information has been given and explained to the subject on all aspects of the clinical investigation that are relevant to the subject's decision to participate.

Prior to enrolling subjects, the site's consent form must be approved by the IRB. The IC document(s) must be controlled (i.e., versioned and dated) to ensure it is clear which version(s) were approved by the IRB. Any adaptation of the sample IC form must be reviewed and approved by Medtronic and the IRB reviewing the application prior to enrolling subjects.

The Investigator must notify the subject (or their legally authorized/designated representative or guardian) of any significant new findings about the study that become available during the course of the study which are pertinent to the safety and well-being of the subject, as this could impact a subject's willingness to participate in the study. If relevant, consent may be requested from subjects to confirm their continued participation.

Subjects will be informed that despite signing the informed consent form, the screening assessment may demonstrate the subject is not a suitable candidate for the study or the procedure and may be withdrawn. Subjects will also be informed that after the investigation visits are completed, the subjects will receive the standard medical care, just as they would have had they not participated in the study.

The template IC form will be provided under separate cover. Prior to initiation of any study-specific procedures, IC must be obtained from the subject (or their legally authorized/designated representative or guardian). Likewise, privacy or health information protection regulation may require subjects to sign additional forms to authorize study sites to submit subject information to the study sponsor. The IC process must be conducted by the Principal Investigator or an authorized designee, and the IC form must be given to the subject (or their legally authorized/designated representative or guardian) in a language he/she is able to read and understand. The process of IC must be conducted without using coercion or undue improper influence on or inducement of the subject to participate by the Investigator or other study site personnel. The IC process shall not waive or appear to waive subject's legal right. The language used shall be as non-technical as possible and must be understandable to the subject and the impartial witness, where applicable.

The subject must have ample time and opportunity to read and understand the IC form, to inquire about details of the study, and to decide whether or not to participate in the study. All questions about the study should be answered to the satisfaction of the subject.

When the subject decides to participate in the study, the IC form must be signed and personally dated by the subject and Investigator or authorized designee, as required by the IC form, and ensured by the Principal Investigator or his/her authorized designee.

***Medtronic Business Restricted***

A copy of the IC form, signed and dated as required by law, must be provided to the subject and his/her authorized designee.

If the IC form is obtained the same day the subject begins participating in study-related procedures, it must be documented in the subject's case history that consent was obtained prior to participation in any study-related procedures. It is best practice for the IC process to be documented in the subject's case history, regardless of circumstance.

The original of the signed IC form must be filed in the hospital/clinical chart and/or with the subject's study documents.

The IC form must be available for monitoring and auditing. Any Medtronic Field personnel who support the Enable Hernia Repair Study must be able to review the subject's signed and dated IC form and verify its completeness prior to proceeding with the procedure. In the event the Medtronic Field personnel identify the IC form as being incomplete, the study procedure will not be allowed to occur until the consent of the subject can be adequately and appropriately obtained.

Consistent with the DoH, vulnerable adults (i.e., those subjects mentally incapable of giving consent) are excluded from this protocol. Any subjects with mental incompetence (e.g., Alzheimer's, dementia, psychiatric disorders, developmental disorders) should be assessed for vulnerable status. If the IC is signed by an individual other than the subject, the monitor may discuss whether the Investigator believes the subject meets the definition of a vulnerable adult. This protocol defines vulnerable adult as those subjects mentally incapable of giving consent, in the Investigator's opinion. The Investigator should consider the definition of vulnerable adult per ISO 14155, which defines vulnerable adults as: "individuals who are unable to fully understand all aspects of the investigation that are relevant to the decision to participate, or who could be manipulated or unduly influenced as a result of a compromised position, expectation of benefits or fear of a retaliatory response. For example, this could include Individuals with loss of autonomy due to immaturity or through mental disability, persons in nursing homes, children, impoverished persons, subjects in emergency situations, ethnic minority groups, homeless persons, nomads, refugees, and those incapable of giving IC. Other vulnerable subjects could include, for example, members of a group with a hierarchical structure such as university students, subordinate hospital and laboratory personnel, employees of the sponsor, members of the armed forces, and persons kept in detention.

## 10.6 Assessment of Performance

The secondary endpoints of this study (**Section 5.2.2**) will assess the overall performance of the Medtronic Hugo™ RAS system when used for inguinal and ventral hernia repair robotic assisted surgery.

## 10.7 Assessment of Safety

Safety will be evaluated through the study primary safety endpoint (one or more procedure- and/or device- related SSEs) and several secondary endpoints (**Section 5.2.2**).

Safety will also be assessed by monitoring the occurrence of AEs, serious adverse events (SAEs), deaths, adverse device effects (ADE), serious adverse device effects (SADE), unanticipated adverse device effects (UADE) or device deficiencies (DD). Adverse event assessments will take place starting with the point of

*Medtronic Business Restricted*

informed consent, through the end of study exit, or until resolution, whichever comes first and will be recorded in the eCRF.

## 10.8 Recording Data

Data entered must be traceable to source documents. Source documentation is defined as all information in original records and certified copies of original records of clinical findings, observations, or other activities in a clinical investigation necessary for the reconstruction and evaluation of the clinical investigation (e.g., hospital records, clinical and office charts, procedure reports, laboratory notes, memoranda, subjects' diaries or evaluation checklists, pharmacy dispensing records, recorded data from automated instruments, copies or transcriptions certified after verification as being accurate copies, microfiches, photographic negatives, microfilm or magnetic media, X-rays, subject files, device data and records kept at the pharmacy, at the laboratories and at medico-technical departments involved in the study).

In general, eCRFs (or paper copies) may not serve as source documents. Source documentation for data elements not routinely captured in medical records may vary from study site to study site; the study site may use source document worksheets if identified as source documents.

The Investigator must ensure the availability of source documents from which the information on the eCRFs was derived. The type and location of source documents should be documented. Where printouts of electronic medical records, are provided as source documents, or where copies of source documents are retained as source documents, those should be certified. Certification must contain (1) the signature of the individual making the copy, (2) the date the copy was made and (3) a statement attesting to the accuracy and completeness of the copy.

The source documents must be made available for monitoring or auditing by Medtronic's representative or representatives of the competent authorities and other applicable regulatory agencies.

The CRF may be considered source for the following data collection elements:

- Enrollment Notification
  - Study site assigned subject reference
- Baseline
  - Administrative information
- AE eCRF
  - Date study site became aware of event
  - Relatedness of adverse event
- DD eCRF
  - Date study site became aware of event
- Subject Death
  - Date study site became aware of death
  - Relatedness of death
- Deviations

***Medtronic Business Restricted***

- Reason for deviation

## 10.9 Deviation Handling

A study deviation is defined as an event within a study that did not occur according to the CIP or the CTA.

The investigator may not deviate from the CIP, unless the deviation is necessary in an emergency situation to protect the rights, safety and wellbeing of the subject. Prior approval by Medtronic is expected in situations where the Investigator anticipates, contemplates, or makes a conscious decision to deviate from the CIP or CTA. Prior approval is not required when a deviation is necessary to protect the safety, rights, or well-being of a subject in an emergency or in unforeseen situations beyond the Investigator's control (e.g., subject failure to attend scheduled follow-up visits, inadvertent loss of data due to computer malfunction, inability to perform required procedures due to subject illness).

For medically justifiable conditions which preempt a subject's ability to complete a study-required procedure, it may be permitted to report only one deviation which will apply to all visits going forward. This may also apply for other unforeseen situations (e.g., the subject permanently refuses to complete a study required procedure and the data will not contribute to the primary end point analysis). However, prior approval from Medtronic is required for such situations.

All study deviations must be reported on the CRF regardless of whether medically justifiable, pre-approved by Medtronic, an inadvertent occurrence, or taken to protect the subject in an emergency. Multiple deviations of the same type at the same visit may be reported on one case report form.

In the event the deviation involves a failure to obtain a subject's consent or is made to protect the life or physical well-being of a subject in an emergency, the deviation must be reported to the IRB as well as Medtronic within five (5) working days. Reporting of all other study deviations should comply with IRB policies and/or local laws and must be reported to Medtronic as soon as possible upon the study site becoming aware of the deviation. Reporting of deviations must comply with IRB policies, local laws, and/or RA requirements.

Medtronic is responsible for analyzing deviations, assessing their significance, and identifying any additional corrective and/or preventive actions (e.g., amend the CIP, conduct additional training, terminate the investigation). Repetitive or serious investigator compliance issues may result in initiation of a corrective action plan with the Investigator and study site, and in some cases, may necessitate suspending enrollment until the problem is resolved or ultimately terminating the Investigator's participation in the study. Medtronic will provide study site-specific reports to Investigators summarizing information on deviations that occurred at the investigational study site on a periodic basis.

Examples of study deviations include but are not limited to:

- Failure to obtain proper IC
- Failure to collect required study data (e.g., required echocardiograms)
- Inclusion/exclusion criteria not met

*Medtronic Business Restricted*

**CONFIDENTIAL**

056-F275 Rev G Clinical Investigation Plan Template

## 10.10 Subject Exit, Withdrawal or Discontinuation

Subjects may voluntarily withdraw from the study at any time. Additionally, the Principal Investigators may withdraw or choose not to enroll subjects if they feel they do not meet the CIP defined inclusion and exclusion criteria or if it is in the best medical interest of the subject in question. If the study Investigator voluntarily removes a subject from further study participation, supporting documentation must be in place for the rationale and date of removal.

In cases of early study exits, all data collected from the time of informed consent to the time of study exit may be used. Subjects who exited early will not be replaced. Enrollment will continue as per CIP definitions up to the predefined maximum number of subjects.

The reason and date for study exit of all enrolled subjects will be documented on the applicable eCRF.

All subjects will be followed per institutional standard of care after any withdrawal, discontinuation, or completion of the study follow-ups.

### 10.10.1 Study Exit

A Study Exit eCRF is required for all subjects. Prior to exiting a subject from the study, it is recommended to follow the subject until all ongoing system and/or procedure related AEs are resolved or unresolved with no further actions planned. Following exit, subjects will continue to receive standard medical care. Upon exiting from the study, no further study data will be collected, or study visits will occur for the subject. All data available through the time of the subject's exit will be used for analysis.

Subjects are urged to remain in the study as long as possible but may be exited from the study for any of the following situations:

- Study completed
- Subject lost to follow-up
- Subject death
- Subject did not meet inclusion/exclusion criteria
- Subject did not provide consent or data use protection authorization
- Subject chooses to withdraw (e.g., consent withdrawal, relocation to another geographic location)
- Investigator deems withdrawal necessary (e.g., medically justified, inclusion/exclusion criteria not met, failure of subject to maintain adequate study compliance)

The following information is required to be collected at study exit:

- Reason for exit

If discontinuation is because of safety or lack of effectiveness, the subject shall be asked to be followed for collecting safety data outside the clinical investigation.

*Medtronic Business Restricted*

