## 9.2 Subject Enrollment

A subject is considered enrolled in the study when the informed consent form is signed and dated. As soon as the surgical procedure has begun with the Medtronic Hugo™ RAS system, the subject must be followed regardless of whether the subject completed the surgical procedure with the Medtronic Hugo™ RAS system. Subject enrollment will be consecutive at the institution according to required procedure types and eligibility criteria. See **Section 14** for additional details.

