## 10.10.3 Lost to Follow-up

Every attempt will be made to contact subjects whose status is unknown, including at a minimum:

- Three phone calls with each attempt clearly documented in the source documents including response or lack thereof.
- If there is no response to the phone calls, then a certified/registered letter should be written to the subject. A copy of the letter should be retained in the subject's source document.

To ensure all efforts have been made, the site should check public health records to identify vital status.

A subject will not be considered lost to follow-up prior to the 1-year visit window closure. A subject would not be considered lost to follow-up until all efforts to obtain current status have been exhausted per the attempts noted above (including review of medical charts and public health records).

In addition, regulation set forth by the governing IRB must be followed.

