## 10.10.5 Investigator Withdraws Subject

No subjects should be withdrawn by Investigators unless compelling medical justification is present. It is recommended Investigators discuss any withdrawals with the study team prior to withdrawing subjects. If an Investigator Withdrawal is necessary, the following data should be collected prior to subject withdrawal if possible:

- Reason for subject withdrawal

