 - 2) for subjects without a relevant event and who missed the 30-day visit but had some other post-procedure visit within the 30-day visit window or at anytime after the 30-day window (e.g., a completed 3-month visit), the subject will be included in the analysis as not experiencing the event. Visits and discontinuations after the 3-month visit will not be considered under this provision.

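### Protocol 10.10 and 10.10.1 allow investigator exit of operated subjects for ineligibility or non-compliance, against 10.10.5 and 9.2, and such exits can thin the denominator of the primary 30-day safety test

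*Protocol*

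**What the plan says.** **Grounds for investigator exit.** Protocol 10.10 says that investigators "may withdraw or choose not to enroll subjects if they feel they do not meet the CIP defined inclusion and exclusion criteria". Protocol 10.10.1 lists unmet criteria as an exit situation and adds an investigator ground: "Investigator deems withdrawal necessary (e.g., medically justified, inclusion/exclusion criteria not met, failure of subject to maintain adequate study compliance". Neither section mentions first incision.

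**Restrictions elsewhere.** Protocol 10.10.5 states: "No subjects should be withdrawn by Investigators unless compelling medical justification is present". Protocol 9.2 says that once surgery with the system has begun, "the subject must be followed regardless of whether the subject completed the surgical procedure with the Medtronic Hugo™ RAS system". Protocol 10.10.3 states: "A subject will not be considered lost to follow-up prior to the 1-year visit window closure".

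**Effect of an exit.** Protocol 10.10.1: "Upon exiting from the study, no further study data will be collected". Protocol 10.10: "Subjects who exited early will not be replaced".

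**Effect on the safety test.** The FAS is fixed at first skin incision (Protocol 14.9, SAP 7.1.3). The primary safety test uses FAS subjects whose 30-day status can be determined, without imputation (Protocol 14.11, SAP 7.4). Under SAP 7.4, a subject with no follow-up visit but a recorded event in the 30 days is counted as an event. An event-free subject is counted as a non-event only if he or she "missed the 30-day visit but had some other post-procedure visit within the 30-day visit window or at anytime after the 30-day window", and visits after the 3-month visit do not qualify. The multiple-imputation, per-protocol and tipping-point analyses in SAP 7.4 and 7.9.1.7 are for effectiveness only. The one safety sensitivity analysis, in SAP 7.1.4, concerns subjects with both hernia types.

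**The concern.** Ineligibility and poor visit compliance are not in themselves medical justifications, so 10.10 and 10.10.1 permit what 10.10.5 forbids. For operated subjects they also conflict with 9.2. The compliance ground sidesteps the purpose of 10.10.3: a subject who misses visits cannot be coded as lost before the 1-year window closes, yet the investigator may exit that subject under another code.

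Ineligibility discovered after incision is foreseeable. Protocol 9.4 excludes subjects whose ventral defect cannot be closed, those needing component separation and those with femoral defects. Each may be settled only during surgery, and SAP 7.1.4 itself anticipates an unexpected femoral hernia. Exits on such grounds could be related to SSE risk.

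At stake is the primary safety comparison with the 30% performance goal in each cohort. If exited subjects go on to have more SSEs than the rest, and those SSEs are never reported, the observed rate is too low, and no planned safety analysis would show it. The effectiveness endpoint is settled at surgery and is largely unaffected.

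**Working it through.** **Inputs.** SAP section 6: performance goal 30%, expected rate 15%, 86 evaluable per cohort, one-sided alpha 0.0125, stated power 86%, 10% attrition, 96 enrolled per cohort. SAP 7.5: Holm steps of 0.0125 and 0.025.

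**1. The plan's own figures.** The exact test passes if events ≤ c, where c is the largest count with P(X ≤ c | n, 0.30) ≤ 0.0125. Power is P(X ≤ c | n, 0.15).
- n = 86: c = 16, exact size 0.0118, power 0.861. This reproduces the stated 86%.
- 86 / 0.9 = 95.6, rounded up to 96, as stated.
- n = 96 (no loss): c = 18, exact size 0.0088, power 0.878.

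Losing the planned 10 subjects lowers power only from 87.8% to 86.1%. The issue is therefore bias, not power.

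**2. False-pass rate under informative exits.** Assumptions, none given in the documents: 96 treated per cohort, a true rate of 30% (96 × 0.30 = 28.8 expected events), k exits dropped from the denominator, and SSE probability q in exited subjects, all unrecorded. The rate among those remaining is (28.8 − kq) / (96 − k), and the false-pass rate is P(X ≤ c) at that rate. Example: k = 10 and q = 0.6 give (28.8 − 6) / 86 = 0.265.

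| Exits k | n | Pass if ≤ | q = 0.3 | q = 0.4 | q = 0.5 | q = 0.6 |
|---|---|---|---|---|---|---|
| 1 | 95 | 18 | 0.0103 | 0.0109 | 0.0115 | 0.0122 |
| 2 | 94 | 18 | 0.0121 | 0.0135 | 0.0151 | 0.0168 |
| 3 | 93 | 17 | 0.0073 | 0.0087 | 0.0104 | 0.0124 |
| 5 | 91 | 17 | 0.0101 | 0.0135 | 0.0179 | 0.0234 |
| 10 | 86 | 16 | 0.0118 | 0.0208 | 0.0355 | 0.0581 |

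The q = 0.3 column is the exact size of the test, with no inflation. The steps between rows come from the discreteness of the exact test.

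**3. Worst case: every exited subject had an unrecorded SSE.**
- 2 exits: 18/94 (p = 0.012, passes) becomes 20/96 (p = 0.029, fails both Holm steps).
- 10 exits at about the assumed 15%: 13/86 (p = 0.001) becomes 23/96 (p = 0.118).
- 10 exits near the literature rates of 3.8% and 4.5% (Protocol Table 14): 4/86 becomes 14/96 (p = 0.0004), still a clear pass.

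**The case against.** The strongest reply is that other provisions already cover most of this.

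- **A reader might infer that the FAS loses subjects.** It does not: membership is fixed at incision. Only the available-data denominator shrinks.
- **A reader might infer that the operator can shape a per-protocol-like set by removing known events.** The documents do not support that. Data up to exit are used (Protocol 10.10.1), and SAP 7.4 keeps recorded events. Keeping exits with events while dropping event-free ones even pushes the observed rate up. Only SSEs that arise after exit and stay unreported can bias it down.
- **A reader might infer that missed-visit exits can come soon after surgery.** Visit 3 (30 ± 7 days) is the first scheduled post-discharge visit, so that path is narrower: Visit 3 missed, then exit before a later qualifying visit.
- **A reader might infer that 10.10.3 is breached.** It is not, because the exit carries a different code. Its purpose is bypassed.
- **A reader might infer that only a reason is collected at exit.** Protocol 10.10 also requires the date, with supporting documentation when the investigator removes the subject. Protocol 12.3 requires unresolved adverse events to be reviewed and updated, and asks for continued follow-up of unresolved related ones. Neither requires a positive statement of SSE status, and neither captures a new SSE after exit.
- **The eligibility ground has an ordinary use before incision.** Enrollment occurs at consent (9.2), and Protocol 14.9 gives ineligibility between consent and surgery as its example. That stands, and it is why limiting the ground to that period costs nothing.
- **The analysis already keeps ineligible operated subjects.** SAP 7.1.4 retains them in the intended cohort, and SAP 7.1.3 removes those who did not meet enrollment criteria from the per-protocol set only. Their exit is therefore unnecessary, but these rules cannot recover data that an exit stops.

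The exit counts and the 40-60% rates have no source in the documents. That objection stands in full.

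**Conclusion.** The contradiction is in the text and should be corrected. An operated subject exited without a recorded SSE before 30-day status is known, or after a missed Visit 3 and before a later qualifying visit, leaves the denominator of a primary test that has no safeguard against informative loss.

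The size is unknown. Under the assumptions in step 2, the false-pass rate against a nominal 1.25% is at most about 1.7% with 1 to 3 exits per cohort, 1.4-2.3% with 5, and 2.1-5.8% with 10. The last case needs the whole attrition allowance to come from these two grounds. There is no inflation if exited subjects share the 30% rate, and the conclusion is robust if observed rates are near the literature 4-5%. This supports a wording correction that should be made, not a claim that the safety result would be invalid.

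**What to change.** Reconcile Protocol 9.2, 10.10, 10.10.1, 10.10.3 and 10.10.5 for operated subjects:

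1. Limit the eligibility exit ground in 10.10 and 10.10.1 to the time before first incision.
2. Remove non-compliance as an exit ground once surgery has begun.
3. After incision, record both as protocol deviations (with per-protocol exclusion for ineligibility, as SAP 7.1.3 already provides) or use conditional disengagement under 10.10.6. Follow-up continues.
4. Leave consent withdrawal and the medical-justification route in 10.10.5 unchanged.
5. For any exit before day 30, record SSE status (event or no event) at the exit date, in addition to the reason, date and adverse-event updates already required.

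The cost is protocol wording, one item on the exit form and a few more contact attempts by sites. Informative loss through consent withdrawal would remain.
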